4.4 Follow-up

All 75 patients will have standard clinical follow-up at 6 weeks, 6 months and 1 year. The clinical information at these visits will be used to identify complications rates that will include lead displacement, rise in capture threshold and lead injury, device related infections.

4.5 Burden/Risk

The main burdens for the patient include:

- The extra time taken to perform the experiments and experimental procedures during their scheduled clinical procedure due to the additional diagnostic investigations. The right heart electro-anatomical mapping will add 10 minutes. The echocardiography will add an additional 5 minutes.
- 2. The extra access in the groin for the mapping catheter and ICE catheter.
- 3. Patients receiving unconventional therapy with conduction system lead implantation

Control Group C: N=25 (Standard of care) I. 12-lead ECG Before the Echocardiogram procedure 3. MRI of the heart I. 12-lead ECG During the 2. Fluoroscopy procedure (x-ray) Routine clinical ca Follow-up 6 weeks, 6 months, 1 v Deleted:

The burden will be mitigated by the minimum extra time being used to complete the experiments, the use of local anaesthetic and the immediate removal of extra research related sheaths as soon as they are not needed

The main risks for the patient are:

A conduction system pacing wire is not known to have a higher complication rate compared to a conventional pacing wire. Conduction system pacing wires have been shown to be as effective as conventional pacing wires at preventing slow heart rates and improving heart pumping. If a complication occurs and the conduction system pacing wire cannot be implanted or does not perform as expected during follow-up a procedure will be performed to convert your pacing system to a conventional pacing system.

The additional risks of vascular tube placement include:

- 1% risk of bruising around the area
- 1 in 1000 risk of damage to the blood vessels requiring surgery
- Less than 1 in 500 risk of stroke

The additional risks of intracardiac echocardiogram include

- 1% risk of bruising around the access area in the leg
- Less than 1 in 1000 risk of heart perforation

The additional risks of electro-anatomical mapping include

Less than 1 in 1000 risk of heart perforation

Therefore, the overall risk of serious complications arising from taking part in the research study are less than 4 in 1000 (0.4%)

Pacemaker implantation involves exposure to ionising radiation to visualise lead implantation. Taking part in this study involves exposure to additional exposure to radiation above the standard clinical procedure due to the additional measurements that will be taken.

lonising radiation can cause cell damage that may, after many years or decades, turn cancerous. We are all at risk of developing cancer during our lifetime. The normal risk is that this will happen to about 50% of people at some point in their life. Taking part in this study will increase the chances of this happening to you from 0.01% to 0.1% (13Gy.cm² (2.1mSv) per patient per procedure).

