4.1 Derivation

The derivation cohort will comprise of 25 prospectively recruited patients. These patients will undergo the research protocol. In these patients, we will attempt to implant a permanent conduction system pacing lead, in lieu of the RV or LV lead. The lead will be implanted by operators who have implanted more than 40 leads to overcome the learning curve.

Pre-implant

Prior to the procedure, patients will undergo a clinically indicated Cardiac MRI. We will use these scans to retrospectively assess for the presence of potential mechanisms which could prevent successful lead implantation, such as the presence of septal fibrosis and chamber dimensions, so that we can assess how these can contribute to challenges at the time of implant. We will also be able to review mechanisms for *successful* implants. This information will be corroborated with data collected from the electro-anatomical maps.

The MRI scans will also be used to merge the anatomical information using CartoMerge to reduce procedure times by building the anatomical geometry prior to the mapping-catheter collecting this information invasively.

During Implant

The participants will undergo the following procedural steps after written informed consent is gained:

- A left infraclavicular incision and axillary access for the lead will be gain as per standard clinical protocol.
- 2. Access from the femoral vein will be sought where a sheath will be placed in the femoral vein to introduce the mapping catheter.
- 3. Fast anatomical mapping (FAM) of the right atrial and right ventricular anatomy will be made where CartoMerge has not already created this anatomy. This will include the right ventricle, the tricuspid valve and the right ventricular outflow tract. Activation and voltage maps will be then be made of the His-bundle area (including the His cloud), right ventricle, right ventricular outflow tract and right ventricular septum.

This will help determine a few key aspects

- 1. Level of conduction system block and therefore guide site of lead deployment
- 2. Anatomy of the right heart and overcome challenges this may propose
- 3. Evidence of septal fibrosis and/or scar that need to be overcome
- 4. Activation pattern of the septum in conduction system block
- 4. Anatomical FAM maps, voltage maps and activation patterns will be compared against the data collected from the cardiac MRI to assess
 - 1. Accuracy of anatomy
 - 2. Fibrosis and scar patterns

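### Section 4.5 puts the added serious risk below 4 in 1000, but the limits it lists sum to 5 in 1000 and no overlap is stated

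*Protocol*

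**What the plan says.** Section 4.5 (Burden/Risk) sets out the added risks of participation by procedure.

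- Vascular tube placement: a 1% bruising risk, then "1 in 1000 risk of damage to the blood vessels requiring surgery" and "Less than 1 in 500 risk of stroke".
- A separate list opens "The additional risks of intracardiac echocardiogram include" and contains "1% risk of bruising around the access area in the leg" and "Less than 1 in 1000 risk of heart perforation".
- A third list opens "The additional risks of electro-anatomical mapping include" and has one entry, the same perforation wording and figure again.

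The section then draws its total: "Therefore, the overall risk of serious complications arising from taking part in the research study are less than 4 in 1000 (0.4" per cent). It does not say that any entries describe the same risk, or that any serious entry is left out.

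Section 4.1 describes how the two catheters are used in the derivation cohort. Step 2 reads: "Access from the femoral vein will be sought where a sheath will be placed in the femoral vein to introduce the mapping catheter". At step 5 the mapping catheter is taken out and the echocardiography catheter goes in through the femoral vein.

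**The concern.** The total is introduced as a consequence of the list above it, so a reader should be able to obtain it from that list. Adding the serious entries gives a higher limit than the one stated. A sum of upper limits is a valid upper limit for the combined risk however the events are related. A lower bound therefore needs a further fact, such as an overlap between entries, and the section supplies none.

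This is the only derived total of added serious procedural risk in the protocol, and the discrepancy makes participation look slightly safer than the list supports. Parts of Section 4.5 address the patient directly, so the figure may also have been used in participant material; that material is not available to check. Nothing in the design or analysis depends on the figure.

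**Working it through.** **Inputs, all from Section 4.5**

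| Added serious risk | Listed under | Limit |
|---|---|---|
| Vessel damage needing surgery | Vascular tube placement | 1/1000 = 0.001 (no 'less than') |
| Stroke | Vascular tube placement | < 1/500 = < 0.002 |
| Heart perforation | Intracardiac echocardiography | < 1/1000 = < 0.001 |
| Heart perforation | Electro-anatomical mapping | < 1/1000 = < 0.001 |

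The two 1% bruising entries are left out as not serious. Either one alone would exceed 0.4%, so the protocol must have left them out too.

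**Step 1. Attempt to reproduce the stated 4 in 1000 from the full list**

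Sum of limits, valid under any dependence between events:

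0.001 + 0.002 + 0.001 + 0.001 = 0.005, that is, less than 5 in 1000 (0.5%).

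Probability of at least one event, if independent:

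1 − (0.999 × 0.998 × 0.999 × 0.999) = 0.00499, or 0.499%.

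Neither gives 0.4%, and rounding does not close the gap.

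**Step 2. Which single changes would give 4 in 1000?**

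- Perforation counted once: 1 + 2 + 1 = 4 per 1000 (0.3995% under independence).
- Vessel damage left out: 2 + 1 + 1 = 4 per 1000 (0.3995%).
- Stroke taken as 1 in 1000 instead of 1 in 500: 1 + 1 + 1 + 1 = 4 per 1000 (0.3994%).

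Leaving stroke out altogether gives 1 + 1 + 1 = 3 per 1000, which does not match. Three different changes reproduce the stated figure, and the text does not indicate which, if any, was intended.

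**Step 3. Size in expected events**

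- All 50 derivation and validation patients having both catheters: limits 50 × 0.005 = 0.25 against 50 × 0.004 = 0.20, a gap of 0.05 of an event. This is an assumption, because Section 4.2 leaves the validation workflow to be derived.
- The 25 derivation patients alone, for whom Section 4.1 specifies both catheters: 25 × 0.001 = 0.025 of an event.

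**The case against.** The best defence is that perforation was counted once, which gives exactly the stated figure. The list is organised by procedure and already repeats an outcome, since bruising appears under both vascular access and echocardiography. Section 4.1 mentions one femoral sheath and no second one, which fits shared access and an author who saw some entries as the same risk listed twice. This reading is possible and cannot be excluded. It remains an inference, however. The two perforation entries stand under separate headings, each described as an additional risk, and the catheters are used one after the other in the same patient, which on a plain reading is two exposures.

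A second defence is that three of the four inputs are upper limits, so a true total below 4 in 1000 is compatible with every entry. For illustration, stroke at 1 per 1000 and each perforation risk at 0.5 per 1000 would give, with vessel damage, 1 + 1 + 0.5 + 0.5 = 3 per 1000. This point stands: the protocol is not shown to understate the true risk. It does not rescue the derivation, because limits of 1, 2, 1 and 1 per 1000 support a combined limit of 5 per 1000 and nothing tighter without more information.

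It is also fair to say that the gap is small, that these are rounded order-of-magnitude figures, and that a clarifying clause might be enough without changing the number.

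**Conclusion.** The concern holds. The bound of 0.4% does not follow from the risks listed in Section 4.5, whose limits sum to 0.5%, and no overlap or exclusion is stated to explain the difference. The gap is 0.1 percentage point between upper limits: 0.025 of an event in the derivation cohort, or 0.05 if all 50 patients in the derivation and validation cohorts have both catheters.

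The sum rests only on treating bruising as not serious and on taking the four remaining entries as separate, as they are presented. The conclusion is limited to the inconsistency between list and total; it does not extend to the true risk. It should be corrected because it is a safety statement about participation, although no endpoint, sample size or analysis changes.

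**What to change.** Make the list and the total in Section 4.5 agree in one of three ways:

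1. If the entries stand and do not overlap, restate the total as less than 5 in 1000 (0.5%).
2. If a component is misprinted, correct it and recompute the total.
3. If entries overlap, for example if the two perforation entries are one risk, say so next to the total.

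Use the same figure in any participant document that repeats it.

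While editing the section, a minor neighbouring sentence also needs attention. After giving a background lifetime cancer risk of about 50%, the protocol says that taking part raises the chance from 0.01% to 0.1%. That cannot be a before-and-after change from a 50% baseline. If a range of added absolute risk is meant, the sentence should say so.

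The cost is a text correction, with no change to design or analysis. Under the first option the stated limit becomes slightly less favourable.

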4.6 Study Outcome Measures

Primary Outcome Measures

1. Success rates of conduction system lead implant (fluoroless workflow vs conventional methods)

Secondary Outcome Measures

- Procedure and fluoroscopy times of the fluoroless workflow vs current conventional methods of His-bundle and Left-bundle pacing
- Procedure and fluoroscopy times of the fluoroless workflow vs conduction system implant to current right ventricular pacing
- 3. Assess capture threshold of His-bundle and Left-bundle pacing from the fluoroless workflow vs that of conventional methods of conduction system implantation
- 4. Number of times leads deployed in the fluoroless protocol vs conventional methods of conduction system implantation
- Complication rates in the fluoroless protocol vs conventional methods of conduction system implantation:

- a. Lead implanted at the incorrect position: non-septal positions
- b. Lead displacement
- c. Lead injury
- d. Rise in threshold (late complication)
- e. Vascular injury
- f. Perforation with or without subsequent tamponade
- g. Device related infection
- h. Pneumothorax

5 Participant Entry

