	9.3	CONFIDENTIALITY	
	9.4	INDEMNITY	
	9.5	Sponsor	
	9.6	Funding	
	9.7	Audits	
10		UDY MANAGEMENT	
11	L PUE	BLICATION POLICY	16
12	2 REF	FERENCES	17

CSP: Conduction system pacing CT: Computed tomography ECG: Electrocardiogram

EGG. Electrocardiogram
EGM: Electrogram
HBP: His-bundle pacing
ICE: Intracardiac echocardiogram
LBBB: Left bundle branch block LBP: Left bundle pacing
LBAP: Left bundle area pacing
LV: Left ventricle
LVAT: Left ventricular activation time

MRI: Magnetic resonance imaging

RV: Right ventricle

TOE: Transoesophageal echocardiogram TTE: Transthoracic echocardiogram

Study Summary

TITLE	Fluoroless Conduction System Implant		
DESIGN	Cohort observational study and interventional at validation phase		
AIMS	Define a feasible fluoroless protocol for conduction system lead implantation		
	Primary Outcomes:		
OUTCOME MEASURES	1. Success rate of conduction system lead implant Secondary Outcomes: 2. Fluoroscopy time 3. Total procedure time 4. Capture threshold 5. Number of times leads deployed 6. Complication rates: a. Lead implanted at the incorrect position: non-septal positions b. Lead displacement c. Lead injury d. Rise in threshold (late complication) e. Vascular injury f. Perforation with or without subsequent tamponade g. Device related infection h. Pneumothorax		

POPULATION	Patients with any indication for a pacemaker
ELIGIBILITY	Main Inclusion Criteria 1. Patients with a ventricular pacing indication: high grade atrioventricular block and symptomatic trifasicular or bifasicular block. (in order to assess the level of conduction system block) 2. Adults willing to take part (ages 18 – 100 years old) 3. Able to give consent.
	Main Exclusion Criteria 1. Unable to give consent 2. Children age < 18 years and adults > 100 years old 3. Pregnant patients 4. Pacing device in situ 5. Indication for cardiac resynchronisation therapy 5.
DURATION	1 year

1. Introduction

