1.1 Background

Discovering how to clinically deliver conduction system pacing efficiently could be a paradigm shift. Early work on conduction system pacing focused on the His bundle, with right atrial mapping for the His signal and deployment of a lumenless pacing lead(1). Left bundle pacing (LBP) then emerged as an alternative, approaching via the basal right ventricular septum to deploy a lead through the septum to capture the left bundle on the left side of the septum(2,3)

Current literature report improved left ventricular function, heart failure outcomes and mortality in conduction system pacing(4,5). Additionally, LBP has a larger target area, can be done with low capture thresholds, has better threshold stability and large amplitude R waves(3). Widespread roll out of conduction system pacing clinically, however, faces three major challenges.

Challenge A1: Identifying target area for lead deployment

Despite growing adoption, conduction system pacing implants remains challenging. Even experienced device consultants take time to learn the technique. Experienced centres achieve implant success of 95%, but centres with new conduction system implanters (but highly experienced pacemaker implanters) have rates as low as 56%(6,7).

Fluoroscopic interpretation is challenging, for several reasons. The target area is smaller than conventional right ventricular pacing, and can be even smaller when there is fibrosis in the septum. The chambers may well be dilated, which displaces not only the fluoroscopic position of the target, but also its orientation. The lead can also be difficult to advance, because of septal fibrosis, unrecognised lead entanglement and unclear trans-septal trajectory. Interpretation of surface ECG and lead data is not straightforward either: there are many levels in the conduction system at which block can occur and it is difficult to distinguish them confidently. Lead entanglement and mal-orientation may be detectable with elaborate equipment such as intracardiac echocardiography (ICE) but we do not know what fluoroscopic or electrical features might provide routine clinical operators with a timely warning. Previous approaches to address these issues have involved normal-heart cadaveric studies which do not give the electrical context of a clinical implant(8).

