1.2 Original Hypothesis

- Conduction system leads can be implanted with almost no fluoroscopy using electroanatomical mapping
- 2. Using electro-anatomical mapping will increase safety of conduction system lead implantation
- The procedure times with electro-anatomical mapping will be less than that of conventional methods using fluoroscopy

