1.3 Rational for Current Study

Currently conductions system pacing can have long fluoroscopy times when compared to conventional right ventricular pacing. This may be due to difficult cardiac anatomy, altered lead trajectory and obstacles such as entanglement, that is not readily visualised with fluoroscopy. As a result operators experience additional cumulative fluoroscopy times. Our study will devise a standardised implantation protocol using 3D electroanatomical mapping systems to reduce both fluoroscopy and procedure times.

2. Study Objectives

Primary Objective

The primary objective of this study is develop a fluoroless implant protocol of conduction system leads using 3D electroanatomical mapping.

Secondary Objective

The secondary objectives will be

- To reduce the overall procedure and fluoroscopy time with utilisation of targeted lead deployment.
- 2. Improve complication rates

3. Recruitment

A total of 75 patients will be recruited for the study

50 patients with a ventricular pacing indication (high grade atrioventricular block and symptomatic trifasicular or bifasicular block) for pacing will be recruited prospectively. The patients will be divided into two groups; 25 patients in the derivation cohort and 25 patients in the validation cohort. The derivation cohort will undergo a detailed research protocol to determine the optimised work flow and this will be applied prospectively to the validation cohort.

The success rates, procedure times, complication rates and fluoroscopy times will be assessed. The 25 patients undergoing conventional methods of conduction system pacing will be recruited as a control arm to compare these outcomes.

In summary, the 75 patients will be grouped as following; 25 patients in the derivation cohort, 25 patients in the validation cohort and 25 patients in the control arm.

4. Methodology

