25 patients will provide the ability to determine the percentage of a successful implant with a precision of a SE (\pm 8%) of a success rate of approximately 80% SD of implant time = SD of total procedure time / $\sqrt{2}$ = 67 / $\sqrt{2}$ =47.37 SE = SD/ $\sqrt{\text{sample size}}$ = 47.37/ $\sqrt{2}$ 5 = 9.47

Data and all appropriate documentation will be stored for a minimum of 5 years after the completion of the study, including the follow-up period.

To assess the primary outcome of the success rates of the conduction system lead implant using the fluoroless workflow developed during our study, ECG information will be collected and capture will be determined by experts.

Fluoroscopy and procedural times will be analysed with one-way ANOVA. Success rates, capture thresholds and battery life will be analysed with t-test.

9 Regulatory issues

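### The t-test named for the primary success comparison does not answer the feasibility question; estimates with confidence intervals would, and they match how n=25 was justified

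*Protocol*

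**What the plan says.** - **Aim and objective.** The Study Summary gives the aim as "Define a feasible fluoroless protocol for conduction system lead implantation". The primary objective in Section 2 is to "develop a fluoroless implant protocol of conduction system leads using 3D electroanatomical mapping".
- **Hypotheses (1.2).** The first is "Conduction system leads can be implanted with almost no fluoroscopy using electroanatomical mapping". The second is "Using electro-anatomical mapping will increase safety of conduction system lead implantation". The third concerns shorter procedure times. None says that implant success will be higher.
- **Primary outcome (4.6).** "Success rates of conduction system lead implant (fluoroless workflow vs conventional methods"). No direction, margin or minimum rate is attached.
- **Sizing (Section 8).** "25 patients will provide the ability to determine the percentage of a successful implant with a precision of a SE" of 8 points at a success rate of about 80%. No power for a comparison is given.
- **Analysis (Section 8).** "Success rates, capture thresholds and battery life will be analysed with t-test". This is the only analysis named for the primary outcome. Neither alpha nor sidedness is stated.
- **Validation (4.2).** Success rates in the 25 validation patients will be assessed, without saying how.
- **Background rates (1.1).** "Experienced centres achieve implant success of 95" per cent; centres with new implanters are put as low as 56%.

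**The concern.** The aim, the sample size and the analysis answer three different questions. The aim asks whether the workflow succeeds often enough. The sample size serves to estimate one success percentage. The named analysis asks whether two success rates differ.

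A t-test of success can reject only the hypothesis of no difference. If it does not reject, nothing follows about whether the workflow works well enough or is not materially worse than conventional implantation. With 25 patients per group, failure to reject is a likely result for a good workflow and for a considerably worse one. The named primary analysis would then say little about the stated aim. This does not depend on using a t-test for yes/no data: Fisher's exact test asks the same question and rejects less often in every case computed below.

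**Working it through.** **Inputs.** From the protocol: 25 validation and 25 control patients (Section 3), planning success of about 80% (Section 8), background rates of 95% and 56% (1.1). Assumed, because the protocol does not say: two-sided alpha 0.05, validation cohort against control as the comparison, and the true rates in each scenario.

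**1. The protocol's own figure.** SE = √(p(1−p)/n) = √(0.80 × 0.20 / 25) = 0.080. The stated 8 points reproduce, but for one group. For the difference between two groups at 80%, SE = √(2 × 0.16 / 25) = 0.113, so the 95% half-width is 1.96 × 0.113 = 0.222, about 22 points.

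**2. How often the named test is significant.** For each of the 26 × 26 possible outcomes, take the pooled t-test p-value on 0/1 data and Fisher's p-value, then add the binomial probabilities of the outcomes with p < 0.05.

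| True success, workflow vs control | t-test significant | Fisher significant |
|---|---|---|
| 80% vs 95% | 38.2% | 19.8% |
| 60% vs 80% | 35.2% | 23.1% |
| 70% vs 80% | 13.5% | 6.9% |
| 100% vs 95% | 3.4% | 0.1% |
| 75% vs 95% | 55.5% | 37.0% |
| 40% vs 80% | 86.7% | 78.8% |

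In the first row the t-test is non-significant in 100 − 38.2 = 61.8% of trials, although the workflow fails four times as often (20% vs 5%). In the fourth row a workflow that never fails is non-significant in 96.6%. The last two rows mark the limit of the argument: large enough deficits are usually detected.

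**3. One possible result, 20/25 vs 24/25.**
- t-test: sample variances 0.1667 and 0.0400, pooled 0.1033; SE = √(0.1033 × 2/25) = 0.0909; t = −0.16/0.0909 = −1.76 on 48 df; p = 0.085.
- Newcombe 95% CI: Wilson limits are 0.609 to 0.911 for 20/25 and 0.805 to 0.993 for 24/25. Lower limit: −0.16 − √((0.80 − 0.609)² + (0.993 − 0.96)²) = −0.354. Upper limit: −0.16 + √((0.911 − 0.80)² + (0.96 − 0.805)²) = +0.031.

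The test reports no significant difference. The interval shows that the data are compatible with a workflow 35 points worse or 3 points better.

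**4. What estimation can deliver at n=25.**
- Newcombe 95% CI for the difference: 24/25 vs 24/25 gives ±15.9 points; 20/25 vs 20/25 gives ±22.1 points.
- With true success of 80% in both groups, the lower Newcombe limit lies above −22 points in 49% of trials and above −16 points in 29%.

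**The case against.** **The harmful inference is not in the text.** A reader might infer that the protocol will treat p > 0.05 as proof of feasibility. It says nothing of the kind. It leaves that reading open, because the t-test is the only named analysis and no rule is set for interpreting it. A missing floor, margin or decision rule could sit in a statistical analysis plan that is not at hand, so that absence is not the point here. The comparison and the test are fixed in the protocol.

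**Estimation is already part of the design.** Section 8 sizes a group to estimate a success percentage, and 4.2 says that validation success will be assessed. So it would be wrong to say that the protocol offers no other basis for judging success. This stands. It also favours the change, since the analysis sentence is what departs from the design.

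**A difference question fits the background.** Section 1.1 presents low success as a challenge that mapping can overcome, and 4.1 expects fewer deployment attempts. That is fair as rationale, but 1.2 does not turn it into a hypothesis. If superiority were meant, 25 per group would not serve it: by the usual normal approximation, 80% power needs 76 per group for 80% vs 95%.

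**The size depends on the assumed rates.** A reader might infer that a workflow failing several times as often would usually escape detection. That is not general: 40% vs 80% (three times the failures) is significant in 87% of trials, and 75% vs 95% (five times) in 56%. What stands is the narrower statement that non-significance is likely over a wide range, including with control at the protocol's own 80%.

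**Conclusion.** The point holds as a mismatch between the named primary analysis and the aim and sizing. At 25 vs 25 the t-test is significant in 38% of trials at 80% vs 95%, 35% at 60% vs 80% and 3% at 100% vs 95%. A non-significant result would therefore not separate a good workflow from a considerably worse one, and it cannot support a claim that the workflow is feasible or not worse.

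The figures rest on two-sided 0.05, on validation against control as the comparison, and on the assumed true rates. The logical point rests on none of these. The documents do not support the stronger charge that the study plans to read non-significance as feasibility. The change is worth making before the validation phase, but it does not call for a different design.

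**What to change.** In Section 8, remove success rates from the t-test sentence and put in its place:

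1. The success proportion in the 25 validation patients with an exact (Clopper-Pearson) 95% CI. For scale, 20/25 gives 59.3% to 93.2%.
2. The validation-minus-control difference in success with a Newcombe 95% CI.
3. A statement that a non-significant difference will not be read as similarity or as feasibility.

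If the sponsor wants a formal claim that the workflow is feasible or not worse, it should set and justify the floor or the margin before the first validation implant. That choice is a judgement for the sponsor, and no value is proposed here.

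**Cost.** Wording only, with no extra patients or data. The price is a narrower conclusion. Even equal observed results leave about ±16 to ±22 points around the difference. With true success of 80% in both groups, a margin as wide as 22 points would be met in only about half of trials (49%). A tighter claim of not being worse would need a larger study.
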